45 criteria of established regulatory standards is proposed for Inova Health Systems.

1 **Safety Considerations:**

2 1) Clinical use of convalescent plasma in this setting is regarded as investigational
3 as the safety and efficacy of convalescent plasma are unproven in the setting of this novel
4 pandemic. Collection and clinical use of this product will be managed as an experimental therapy
5 consistent with ethical safeguards (informed consent of donors and recipients, FDA approval
6 through IND pathway, institutional approval, and special labeling).

7 2) Procedures will maximize safety of both plasma donors and recipients.

8 a. Standard blood donation protocols and screening will be followed (Donor History
9 Questionnaire, Appendix E)

10 b. Potential donors will be assessed by physician or nurse practitioner to assure clinical
11 stability and full recovery (confirmed by nucleic acid amplification technology (NAT))
12 prior to donation

13 c. Plasma collections must be separated by \geq 28 days, eligibility must be re-evaluated at each
14 collection, and total volume collected will be based on estimated donor blood volume in
15 accordance to guidelines for healthy donors

16 d. As with other plasma therapies, ABO compatibility will be assured

17

18

19 e. Potential risks to convalescent plasma recipients will be discussed in the informed consent
20 process and monitored for closely in the hospital setting:

21 i. risk of unintended transmission of relevant transfusion transmitted diseases from
22 donor

23 ii. risks of transfusion related reactions

24 iii. theoretical risk of immune enhancement due to transferred antibodies that could
25 exacerbate the disease

26

27

28

29

30

31

32

33

34

35

36

37

1 Plasma Collection and Storage: Collection, storage, and preparation of plasma will be performed by the
2 Inova Blood Center Staff. The plasma product is to be handled like a regular or licensed FFP/FP24, with
3 special labeling. Convalescent plasma will be stored at the Inova Blood Donor Services Facility, the
4 largest hospital based donor center in the country. It is a well-established and regulated BSL2 facility
5 which is CLIA/CAP certified in full compliance with regulatory guidelines including AABB, FDA, with
6 use of good manufacturing practices.

7 The Inova Blood Center Staff are routinely engaged in automated plasma collection and preparation in

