4 will be performed to permit retrospective determination of the characteristics of an effective product and
5 dosage regimen, and the characteristics of patients most likely to benefit¹⁸.

6 Data and blood specimen will be banked for future use pursuant to the IRB Approved Inova COVID-19
7 Biobanking Protocol. We will follow the guidelines and procedures for specimen storage and access as
8 described in the IRB approved Inova COVID-19 Biobanking Protocol.

9 Specimens will be stored at the Office of Research at Inova Biobank with standard certifications in place.

10

1 **PLASMA RECIPIENTS:**

2 **Inclusion Criteria for Recipients of COVID-19 Convalescent Plasma:**

3 Patients in the Inova Health System with confirmed COVID-19 by PCR testing

4 Age \geq 13 years

5 Currently hospitalized with COVID-19 infection with severe or life-threatening clinical syndrome²² as
6 follows:

7 Severe COVID-19: (three or more of the following)

8

- 10 • Dyspnea
- 11 • Respiratory rate \geq 30/min
- 12 • Blood oxygen saturation (SpO₂) \leq 94% on room air
- 13 • Partial pressure of arterial oxygen to fraction of inspired oxygen (P:F) ratio $<$ 300
- 14 • Pulmonary infiltrates $>$ 50% of lung parenchyma within 24 to 48 hours

15 Life-threatening disease is defined as: (one of the following)

- 16 • Respiratory failure
- 17 • Septic shock, and/or
- 18 • Multiple organ dysfunction or failure

19 Patient must provide informed consent or have health care power of attorney/next of kin provide consent
20 if he/she cannot.

21 **Exclusion Criteria:**

22 Contraindication to receive plasma as deemed by the treating physician

23 Severe hypercoagulable state (documented in medical chart or by treating physician assessment)

24 Absolute IgA deficiency

25 Prior history of Transfusion Related Acute Lung Injury (TRALI)

26 Inability to tolerate plasma volume due to severe systolic or diastolic heart failure despite slower infusion
27 and diuretic administration

28 Positive pregnancy test (HCG)

29 **Recipient Screening Labs**

30 Blood Type

31 Total immunoglobulin (Ig) levels: IgG, IgA, IgM

32 Coagulation tests to include PT/INR and PTT

33 Complete blood count and differential

34 **Pre-Treatment Testing:**

35 Optional Blood draw for Inova COVID-19 Biobank (up to four tubes each) prior to each dose of plasma

36 **Target Recipient Recruitment:** 150-200 individuals

37 **Primary Endpoints:**

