25 appropriate. Treating physician will notify the study doctor and staff if there is an adverse reaction.

26 Possible anticipated infusion related reactions could include:

27 1) Transfusion Associated Circulatory Overload – dose of intravenous furosemide may be
28 considered
29 2) Transfusion-Related Lung Injury- supportive care as directed by treating physician
30 3) Allergic Reaction/Anaphylaxis – additional dose of diphenhydramine, dose of intravenous or oral
31 corticosteroids or intramuscular epinephrine could be considered
32 4) Transmission of transfusion transmitted diseases – supportive care or targeted treatment if
33 infection identified
34 5) Febrile Transfusion Non-hemolytic Transfusion Reaction – supportive care

35 These adverse events, if present, will be recorded by clinical research team.

36

37 **Post-Treatment Blood Draws:**

38 Optional blood draws (up to four tubes) may be drawn on days 7, 14, 21, and 28 (+/2 days) following each
39 dose of convalescent plasma where feasible for Biobanking.

40 If patient is discharged prior to 7 days post-dosing, then follow-up phone call or email assessments
41 will be made by study staff at 7 days, 14 days, 21, and 28 days (+/2 days) following the original dose.

1
2 **Script for Phone Call(s) or Email(s) to Recipients (if applicable):**

3 1) Are you in a home environment (your home or family member's home)?
4 2) If not, are you in a nursing or rehabilitation facility?
5 3) Are you using oxygen?
6 4) Have you required an urgent care or emergency room visit for any reason since your
7 discharge?
8 5) Have you required re-hospitalization for any reason since your discharge?

9
10 **Trial Methods**

11 Convalescent plasma will be made available to patients hospitalized in the Inova Heath System.

12
13 Patient outcome monitoring and reporting will include indicators of safety and efficacy. Case Report
14 Forms will be used to capture essential data.

15
16 **Statistical Plan**

17 Study parameters (e.g., clinical status scale, death, hospitalization, etc.) will be described using traditional
18 descriptive statistics (median [IQR], frequency and percent). Data will be assessed for 'missingness' with
19 parameters exceeding 10% missing explored for imputation (e.g., multiple imputation, last value carried
20 forward, etc.). Departures from normality will be assessed via Shapiro-Wilkes test with data

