21 transformations explored as needed. All analyses will be conducted using SAS (version 9.4, Cary, NC)
22 with p<0.05, two-tailed considered statistically significant.

23
24 Primary efficacy endpoints:

25 1. Gilead 7-point scale – For each time point (day 0 vs. 7), summary clinical status scores will be
26 calculated. Changes in scores will be subsequently assessed via a generalized linear mixed model
27 with clinical status assessed at day 0 vs. 7. A statistically significant increase of ± 2 points in β
28 from day 0 to day 7 will be considered as evidence of efficacy. A mixed model allows for
29 examination and inclusion of the variance-covariance matrix into the model as a result of expected
30 within-subject serial correlation as a result of repeated assessments over time.
31 2. Plasma transfusion related adverse events will be scored as 1+ vs. 0 and will be assessed via Chi-
32 Square test with a hypothesized distribution of expected AE (using the higher incidence estimate):
33 i. Transfusion Associated Circulatory Overload: 1:1,566 to 1:68 plasma units
34 transfused
35 ii. Transfusion-Related Lung Injury: 1:1,200 to 1:190,000
36 iii. Allergic Reaction/Anaphylaxis: 1-3%
37 iv. Febrile Transfusion Non-hemolytic Transfusion Reaction: 0.1-1%

38
39 Secondary endpoints:

40 1. Change in 7-point ordinal scale score and SOFA score over time will be assessed via individual
41 growth models (IGM). Times will be day0, 14, 21, and 28
42 2. Mortality will be assessed via Chi-Square test with a hypothesized current mortality rate of 1-5%
43 (age adjusted).
44 3. Need for mechanical ventilation for those not ventilator at time of plasma infusion will be
45 assessed via Chi-Square test with a currently available published estimates.

1 4. Time to discontinuation of supplemental oxygen, time to liberation from mechanical ventilation,
2 duration of hospitalization will be summarized as median (IQR) or rates and compared to currently
3 available published estimates.
4
5

6 **ADVERSE EVENTS AND TOXICITY MANAGEMENT**

7 **Definitions of Adverse Events and Serious Adverse Events**

9 **Adverse Events (AE)**

10 An AE is any untoward medical occurrence in a clinical study subject administered an investigational
11 product, which does not necessarily have a causal relationship with the treatment. An AE can therefore be
12 any unfavorable and/or unintended sign, symptom, or disease temporally associated with the use of an

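### The plan holds reference rates for circulatory overload and lung injury but never compares the accumulating count with them during enrolment, and names no count that prompts review

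*Combined protocol and SAP*

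**What the plan says.** Safety Considerations, item 1, treats the product as investigational "as the safety and efficacy of convalescent plasma are unproven in the setting of this novel" pandemic. Infusion reactions within 6 hours are the second primary endpoint. Target Recipient Recruitment is "150-200 individuals", and the Dosing section allows one dose plus up to two more.

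The Statistical Plan, Primary efficacy endpoints, item 2, reads "Plasma transfusion related adverse events will be scored as 1+ vs. 0 and will be assessed via Chi"-"Square test with a hypothesized distribution of expected AE (using the higher incidence estimate"). Two of the listed references are "Transfusion Associated Circulatory Overload: 1:1,566 to 1:68 plasma units" transfused and "Transfusion-Related Lung Injury: 1:1,200 to 1:190,000". Significance is judged "with p<0.05, two-tailed considered statistically significant". No time is given for this test and no interim look is mentioned.

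For individual recipients, the Safety section provides monitoring during infusion, 24 hours of in-hospital observation, and notification of the study doctor and staff by the treating physician when a reaction occurs. After the list of possible reactions it adds: "These adverse events, if present, will be recorded by clinical research team". The section titled Adverse Events and Toxicity Management contains only the definitions of adverse and serious adverse events; expedited reporting appears only inside the second definition.

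**The concern.** Some overload is expected with any plasma. A single case can look ordinary at the bedside even when cases are arriving several times too often, because an excess shows only in the count set against its denominator. The plan has the benchmark, the event definition and staff who record the events. It does not say when the count is set against the benchmark during enrolment, who does this, or what result prompts a review.

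If this product causes more overload than ordinary plasma, the plan as written has no defined point at which that would be recognised before the remaining recipients are exposed. The trial is open-label with a single arm, so a running tally breaks no blind.

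**Working it through.** The documents state no power, interim look or boundary for this endpoint, so there is no figure of the plan's own to reproduce.

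**Inputs from the plan.** Overload 1/68 = 1.471% per unit. Lung injury 1/1,200 = 0.083%; its denominator is not named and is taken here as per unit. Recipients 150 to 200, with 1 to 3 doses each: 150 to 600 infusions.

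**Assumptions.** One unit per infusion, independent infusions, correct attribution of events. The true rates of 3%, 5% and 8% are illustrative; none is in the documents.

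**Expected counts.** p0 = 1/68 + 1/1,200 = 0.01554. Over 200 infusions, 200 × 0.01554 = 3.1 events; over 600, 9.3. At a true 8%, 200 × 0.08 = 16.

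**The planned test.** With one unit each, overload is expected in 150/68 = 2.2 to 200/68 = 2.9 recipients. The uncorrected chi-square, (x − np)²/[np(1 − p)] > 3.84, rejects upward at 6 of 150 or 7 of 200. Its power is 65% or 78% at a three-fold excess, and 97% or 99% at five-fold. So the test can find an overload excess, but the plan does not say that it will be applied before enrolment is complete. For lung injury the expected count is only 0.125 to 0.167. The chi-square would reject on a single event, which has probability 11.8% (150) or 15.4% (200) at the reference rate. An exact test needs 2 events and has power of only 13% or 20% at a five-fold excess.

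**A running check.** Look after every 25 infusions. Flag at the smallest k with P(X ≥ k | n, p0) < 0.05, X binomial.

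| Infusions n | Flag at k | P(X ≥ k) at p0 |
|---|---|---|
| 25 | 3 | 0.007 |
| 50 | 3 | 0.043 |
| 75 | 4 | 0.030 |
| 100 | 5 | 0.020 |
| 125 | 5 | 0.046 |
| 150 | 6 | 0.031 |
| 175 | 7 | 0.020 |
| 200 | 7 | 0.038 |

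The same formula gives 8 at 225 and 250, 9 at 275 and 300, 10 at 325 and 350, 11 at 375, 12 at 400 and 425, 13 at 450 and 475, 14 at 500 and 525, 15 at 550 and 575, and 16 at 600.

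**Cumulative probability of a flag.** At each look, add the binomial count from the next 25 infusions to the paths not yet flagged, and remove the paths that reach k:

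| True rate | By 50 | By 100 | By 200 |
|---|---|---|---|
| 1.55% (reference) | 0.04 | 0.06 | 0.093 |
| 3% | 0.19 | 0.28 | 0.50 |
| 5% | 0.46 | 0.66 | 0.91 |
| 8% | 0.77 | 0.94 | 0.998 |

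At the reference rate the false-flag probability rises to 0.13 by 450 infusions and 0.145 by 600.

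**Lung injury alone.** Overload at reference and lung injury five-fold gives 1/68 + 5/1,200 = 1.89%. The flag probability is 0.097 by 100 infusions and 0.16 by 200, against 0.058 and 0.093 with no excess. At ten-fold it is 0.28 by 200.

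**The case against.** The strongest reply is that safety oversight exists. The study doctor hears of every reaction and, in an open-label trial, could know the running total. Trial Methods promises outcome monitoring that includes safety indicators. The background places the study under FDA supervision through an IND, and the serious adverse event definition calls for judgement on expedited reporting. This stands as far as it goes: single cases are not unseen. But none of these provisions gives an interval, a reviewer, an expected count or a consequence, so the missing piece is the comparison of the count with its reference.

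A second reply concerns the tally. It pools two reactions, and overload dominates. That is correct: a pooled count is a weak instrument for lung injury, and individual review has to carry that part.

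A third is attribution. Recipients may already be in respiratory failure, and progression of COVID-19 can resemble an infusion reaction. A rate for plasma in general may also not fit these patients. Both could push the count above reference without harm from the product, so the quoted false-flag probabilities are probably too low. Repeat infusions in one recipient are also unlikely to be fully independent.

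Finally, 8% is about five times the reference and favours the tally. At 3%, about twice the reference, the chance of a flag by 200 infusions is only one half.

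**Conclusion.** The point holds as a gap in aggregate safety review. The reference rates are used in one test with no interim look stated, and no section sets the accumulating count against them or names a count that prompts review. For overload the gap is material: the tally flags a true pooled rate of 5% with probability 0.91 within 200 infusions, and a rate of 8% with probability 0.77 within 50.

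A reader might infer three stronger things that the documents do not support. One is that reactions would go unreviewed; each is notified to the study doctor. Another is that the chi-square is declared a final analysis; its timing is not stated, and an end-of-study test is inferred from the absence of any earlier look. The third is that a running count would protect against excess lung injury; a five-fold excess alone raises the flag probability by 200 infusions only from 9% to 16%.

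The figures rest on independent infusions, correct attribution, one unit per infusion, and a per-unit reading of the lung-injury rate.

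**What to change.** Add to the Statistical Plan and the adverse-event section:

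- The denominator is infusions, counted over all doses (up to about 600). This matches the per-unit overload rate and removes the ambiguity of scoring a recipient who has had several doses as 1+ or 0.
- After every 25 infusions, cumulative overload plus lung injury is compared with 1.55% per infusion. It flags at 3 events by 25 or 50 infusions, 4 by 75, 5 by 100 or 125, 6 by 150, 7 by 175 or 200, and so on by the same rule to the last infusion.
- A flag prompts a prompt, documented review by the investigator with the IRB and under the IND. It is a trigger for review of the trial and does not govern treatment of any recipient. Whether enrolment pauses meanwhile is for the sponsor and IRB to specify in advance.
- Every lung-injury case, and every death judged infusion-related, receives its own documented review whatever the tally shows.

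The planned comparison with reference rates stays for reporting.

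The cost is protocol wording and a periodic count by staff who already record these events, with no new committee and no change in sample size. The downside is a 9% to 15% chance of an unnecessary review, depending on the number of infusions, and more if disease progression is attributed to the infusion. If the sponsor and IRB choose to pause enrolment during a review, the delay is a further cost.

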38 1) Change in clinical status as captured by 7-point ordinal scale score (being utilized in Gilead Sciences
39 remdesivir trial^{19, 20}) at time of plasma infusion (day 0) compared to day 7:

40

- 44 1. Death
- 45 2. Hospitalized, requiring mechanical ventilation or ECMO

- 1 3. Hospitalized, requiring non-invasive ventilation or high flow oxygen
- 2 4. Hospitalized, requiring supplemental oxygen
- 3 5. Hospitalized, not requiring supplemental oxygen--requiring ongoing medical care
- 4 (COVID-19 related or otherwise)
- 5 6. Hospitalized, not requiring supplemental oxygen-not requiring ongoing medical care
- 6 (COVID-19 related or otherwise).
- 7 7. Not Hospitalized

8 2) Adverse events related to plasma infusion (within 6 hours of infusion) to include²³:

- 9 a) Transfusion-related events
 - 10 i. Transfusion Associated Circulatory Overload
 - 11 ii. Transfusion-Related Lung Injury
 - 12 iii. Allergic Reaction/Anaphylaxis
 - 13 iv. Transmission of transfusion transmitted diseases
 - 14 v. Febrile Transfusion Non-hemolytic Transfusion Reaction

15 Secondary Endpoints:

- 16 3) Change in 7-point ordinal scale score (being utilized in Gilead Sciences remdesivir trial) from time
- 17 of plasma infusion (day 0-prior to first infusion) to days 14, 21, and 28^{19,20}.
- 18 4) SOFA score at days 0, 7, 14, 21, 28²¹
- 19 5) Time to discontinuation of supplemental oxygen
- 20 6) Duration of hospitalization
- 21 7) Time to liberation from mechanical ventilation (for patients on a ventilator)
- 22 8) Need for mechanical ventilation (For those not on the ventilator)
- 23 9) All-cause Mortality [at 28 days]

24 ○

| Organ System, Measurement | SOFA Score | | | | |
|--|------------|-------------------|--|--|---|
| | 0 | 1 | 2 | 3 | 4 |
| Respiration PaO ₂ /FiO ₂ , mmHg | Normal | <400 | <300 | <200 (with respiratory support) | <100 (with respiratory support) |
| Coagulation Platelets x10 ³ /mm ³ | Normal | <150 | <100 | <50 | <20 |
| Liver Bilirubin, mg/dL (μmol/l) | Normal | 1.2-1.9 (20-32) | 2.0-5.9 (33-101) | 6.0-11.9 (102-204) | >12.0 (<204) |
| Cardiovascular Hypotension | Normal | MAP<70 mmHg | Dopamine ≤5 or dobutamine (any dose)** | Dopamine >5 or epinephrine ≤0.1 or norepinephrine ≤0.1 | Dopamine >15 or epinephrine >0.1 or norepinephrine >0.1 |
| Central Nervous System Glasgow Coma Score | Normal | 13-14 | 10-12 | 6-9 | <6 |

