| Renal Creatinine, mg/dL (μmol/l) or Urine output | Normal | 1.2-1.9 (110-170) | 2.0-3.4 (171-299) | 3.5-4.9 (300-440) or <500 mL/day | >5.0 (>440) or <200 mL/day |

26 * Source: [Vincent et al., 1996](#).

- 27 10) All other adverse and serious adverse events will be recorded as well (see adverse events section to follow).
- 28 11) Change in standard of care inflammatory markers (ferritin, LDH, CRP, D-dimer) where available
- 29 from day 0 to days 7, 14, 21, 28.

1 Exploratory Endpoints:

2 12) Association between antibody levels and donor characteristics/clinical course
3 13) Association between clinical response in recipients and antibody levels in the donors

4

5 **Dosing:**

6 • One dose of 200-300mL (standard collection bag volume) of convalescent plasma will be infused
7 over approximately one hour intravenously with standard vital sign monitoring per unit protocol
8 and standard of care for plasma infusion.

9 • Up to two additional doses of 200 mL of convalescent plasma may be administered within 14 days of initial
10 dose at 1-7 day intervals according to disease severity and tolerance of the infusions. Where possible,
11 plasma from distinct donors will be used for additional doses.

12 • To reduce probability of allergic reaction, pre-medication with diphenhydramine 25mg orally or
13 intravenously will be given within 2 hours before each dose of plasma, unless there is a
14 contraindication noted by treating physician.

15 • Slower infusion time of two hours with optional dose of 20mg intravenous furosemide after first
16 hour can be considered for patients at risk for transfusion-associated circulatory overload

17 • Infusion can be slowed for patient comfort at any time.

18 **Safety:** Patients will be monitored closely during plasma infusion per Inova nursing policy titled
19 “Transfusion/Infusion of Blood Components” Version 01.01. Patients will remain in the hospital for a minimum
20 of 24 hours post-infusion with vital signs performed per standard of care with frequency based on the
21 treating hospital unit. Patients will be discharged from hospital according to standard of care any time
22 after completion of 24 hour observation period post-infusion dosing.

23 If oxygenation worsens post-infusion, treating physician will perform assessment as to the presence of a
24 transfusion related reaction, increase oxygen delivery, and obtain portable chest film if deemed clinically

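### Infusion-reaction safety, a primary endpoint, rests on a chi-square test against expected rates with no confidence limit; at 150-200 recipients that test is a poor basis for a safety conclusion

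*Combined protocol and SAP*

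**What the plan says.** Primary Endpoints, item 2 reads "2) Adverse events related to plasma infusion (within 6 hours of infusion) to include" and then lists the reactions. The analysis is under Statistical Plan, Primary efficacy endpoints, item 2: "Plasma transfusion related adverse events will be scored as 1+ vs. 0 and will be assessed via Chi", continuing "Square test with a hypothesized distribution of expected AE (using the higher incidence estimate". For overload the reference is "Transfusion Associated Circulatory Overload: 1:1,566 to 1:68 plasma units" transfused. The higher estimates for the other reactions are 1:1,200 for lung injury, 3% for allergic reaction and 1% for febrile reaction.

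The general rule for all analyses is "with p<0.05, two-tailed considered statistically significant". The opening of the Statistical Plan also calls for frequencies and percents of study parameters.

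The recipient target is "150-200 individuals". Under Dosing, each recipient gets a first dose ("One dose of 200-300mL (standard collection bag volume) of convalescent plasma will be infused"), and then: "Up to two additional doses of 200 mL of convalescent plasma may be administered within 14 days of initial" dose. A recipient may therefore have one to three infusions.

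For this endpoint the documents give no confidence interval, upper bound, unacceptable rate or power. They do not say whether patients or plasma units are counted, or whether the binary score is formed per reaction or over all reactions together.

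**The concern.** In a single-arm study with fixed reference rates, the useful safety question is how large an excess the data can rule out. A p-value against the reference rate does not answer it. With few expected events a non-significant result is likely even when the true rate is well above the reference, and the p-value gives no sign of how far above it could be. Choosing the higher incidence estimate as the null makes an excess harder still to detect. For the rarest reaction the same test fails in the other direction, because its large-sample approximation does not hold.

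The protocol describes the product's safety as unproven in this setting, and this is one of two primary endpoints. As planned, the inferential result would not tell a reader which reaction rates the study excludes.

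**Working it through.** The plan states no power or detectable excess, so there is no figure of its own to reproduce. The doubling used below is an assumption of this review.

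**Inputs.** Reference rates p0 from Statistical Plan item 2: overload 1/68 = 1.47%, lung injury 1/1,200 = 0.083%. N = 150 and 200 from the recipient target. From Dosing, three infusions each would give 3 x 150 = 450 or 3 x 200 = 600 units. Two-sided alpha is 0.05.

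**Test.** One-sample Pearson chi-square on 1 df: X² = (k - n·p0)² / [n·p0·(1 - p0)], significant if X² > 3.84. The miss probability is the exact binomial probability of a non-significant count at the true rate.

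**Overload, true rate doubled to 2/68 = 2.94%**

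| Units | Expected at 1/68 | Significant excess from | Missed |
|---|---|---|---|
| 150 | 2.21 | 6 | 71.9% |
| 200 | 2.94 | 7 | 62.5% |
| 450 | 6.62 | 12 | 33% |
| 600 | 8.82 | 15 | 23% |

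At n = 150, k = 5 gives X² = 3.59 and k = 6 gives 6.62. At n = 200, k = 6 gives 3.23 and k = 7 gives 5.68. Because counts are discrete the miss rate is not monotone in N. The cut-off stays at 6 up to N = 188, where the miss rate reaches its low of 52%, and then moves to 7. The range over N = 150-200 is therefore 52-72%. The 450 and 600 rows treat infusions in the same patient as independent.

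**What a non-significant overload count leaves open.** Exact (Clopper-Pearson) two-sided 95% upper limit at the largest non-significant count:

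- 5/150: 7.6%, and 7.6/1.47 = 5.2 times the reference
- 6/200: 6.4%, 4.4 times
- 11/450: 4.3%, 2.9 times
- 14/600: 3.9%, 2.6 times

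At close to the expected count the limits are 4.7% for 2/150 (3.2 times) and 4.3% for 3/200 (2.9 times), so a doubling is not excluded there either.

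**Lung injury.** Expected events: 150/1,200 = 0.125 and 200/1,200 = 0.167. One event gives X² = 6.13 at N = 150 and 4.17 at N = 200, both significant. At exactly the reference rate the chance of at least one event is 1 - (1 - 1/1,200)^150 = 12%, and 15% at N = 200, so the nominal 5% test has a false-alarm rate of 12-15%. With zero events the exact upper limits are 2.4% and 1.8%, or 29 and 22 times the reference. An exact binomial test would need two events.

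**Pooled reading.** If the binary score means any reaction versus none, the expected rate is 1/68 + 1/1,200 + 0.03 + 0.01 = 5.55%, assuming no overlap. Doubling overload alone raises it to 7.02%. The cut-offs are 14/150 and 18/200, and the doubling is missed about 83% of the time at either size.

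**The case against.** The plan gives a test and an alpha, and says nothing about what p>=0.05 would mean. A reader might infer that a non-significant result will be reported as reactions occurring at the expected rate. The documents do not say so. The same list does state what counts as evidence of efficacy for the ordinal scale but offers no counterpart for safety. That objection stands: the fault is an undefined interpretation, not a stated wrong one.

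A reader might also take a 62-72% miss rate as unconditional. It is not. It needs one infusion per recipient and describes only the two ends of the target. The reference is per unit, and with repeat doses the miss rate can fall to 23%.

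Nor do the figures support saying that a several-fold excess of lung injury would most likely be missed. Under the plain chi-square a 5-fold excess is missed 53% of the time at N=150 and 43% at N=200, so at N=200 it is flagged more often than not. Larger excesses of the commoner reactions are usually detected: a tripling of overload is missed 35% / 22% of the time, and a tripling of allergic reactions 7% / 2.5%. The pooled reading is only one possibility. Four separate reference rates suggest separate tests at least as naturally.

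Finally, counts and percents are planned and reactions are recorded, so events are not hidden and a reader could derive exact limits. This is true, but it leaves the primary safety inference to the reader. It does not answer the overload limits, which exceed twice the reference even at 600 units, or the invalid approximation for lung injury.

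**Conclusion.** The concern holds in limited form. The only planned inference for primary endpoint 2 is a p-value that, at 150-200 recipients, does not show which reaction rates the data exclude. For overload it has low power against a doubling with one infusion each, and moderate power at best with three. A non-significant count remains compatible with 2.6 to 5.2 times the reference, depending on the number of units. For lung injury neither outcome is a sound basis for a conclusion at 150-200 units: a single event is flagged by an invalid approximation, and no events leaves 22 to 29 times the reference open.

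These figures assume each reaction is tested alone against its higher estimate, without continuity correction (with it, the overload range over N=150-200 is 63-78%), and that units are independent. The doubling is illustrative; the documents name no excess of interest. The data stay usable, so this is a change that should be made to the analysis and its wording, not a flaw that invalidates the study.

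**What to change.** In Statistical Plan, Primary efficacy endpoints, item 2:

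- Replace the chi-square p-value as the basis of the safety conclusion. For each reaction separately, report the observed rate with its exact (Clopper-Pearson) 95% confidence interval beside the reference range.
- State whether patients or plasma units are the denominator. If units, allow for repeated infusions within a patient, since the simple exact interval assumes independence.
- State that p>=0.05 is not evidence of no excess, and word the conclusion as the highest rate the data exclude.
- If any test is kept, use an exact binomial test.
- Keep any pooled any-reaction result descriptive.

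A margin fixed before the data are examined is needed only if the sponsor intends to claim no excess.

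The cost is analysis-plan wording and a few lines of SAS, with no extra patients, visits or data. The downside is a less favourable safety statement: it will show that several-fold excesses of overload and lung injury cannot be excluded.
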